1.2 Adverse Event Reporting

Adverse Events may be spontaneously identified by the patient and/or in response to an open question from study personnel or revealed by observation, physical examination, or other diagnostic procedures. Any clinically relevant deterioration in laboratory assessments or other clinical finding is considered an AE. When possible, signs and symptoms indicating a common underlying pathology should be noted as one comprehensive event.

The Sponsor-Investigator, is responsible for reporting adverse events (AEs) to any regulatory agency, to the Sponsor-Investigator's IRB and to the Investigational Drug Sponsor.

1.3 Serious Adverse Event Reporting

Generally, any AE considered serious by the PI or Sub-investigator or which meets the definition of an SAE included in **Section 12.2, Definition of Serious Adverse Events**.

SAEs will be captured on the appropriate case report form (CRF) as well as in the Serious Adverse Event reporting section in Velos, a HIPAA AND 21 CFR part 11 compliant database and will be reported to the University of Miami's IRB per institutional requirements.

According to 21 CFR 312.32(c)(1), "the sponsor must notify FDA in an IND safety report of potential serious risks, from clinical trials or any other source, as soon as possible, but in no case later than 15 calendar days after the sponsor determines that the information qualifies for reporting... In each IND safety report, the sponsor must identify all IND safety reports previously submitted to FDA concerning a similar suspected adverse reaction and must analyze the significance of the suspected adverse reaction in light of previous, similar reports or any other relevant information. The sponsor must report any suspected adverse reaction that is both serious and unexpected. The sponsor must report an adverse event as a suspected adverse reaction only if there is evidence to suggest a causal relationship between the drug and the adverse event, such as:

- (A) A single occurrence of an event that is uncommon and known to be strongly associated with drug exposure (e.g., angioedema, hepatic injury, Stevens-Johnson Syndrome);
- (B) One or more occurrences of an event that is not commonly associated with drug exposure, but is otherwise uncommon in the population exposed to the drug (e.g., tendon rupture);

IRB Study Number: 20210641
Version #4, Date: October 26, 2021

(C) An aggregate analysis of specific events observed in a clinical trial (such as known consequences of the underlying disease or condition under investigation or other events that commonly occur in the study population independent of drug therapy) that indicates those events occur more frequently in the drug treatment group than in a concurrent or historical control group.”

Furthermore, according to 21 CFR 312.32(c)(2), “the sponsor must also notify FDA of any unexpected fatal or life-threatening suspected adverse reaction as soon as possible but in no case later than 7 calendar days after the sponsor's initial receipt of the information.”

Serious Adverse Events

Serious criteria are applied by the Investigator to each AE as specifically defined below. These criteria are used to determine whether an AE is serious or non-serious. The assessment is made independently of severity assessment. For example, the development of a severe rash that occurs after signing of the ICF may not meet serious criteria as defined below and therefore would be considered a severe, non-serious AE.

Any AE that meets any 1 of the following 6 criteria is considered an SAE:

- The outcome of the AE is death
- The AE is immediately life threatening. Life threatening means that the patient is, in the opinion of the Investigator, at immediate risk of death from the reaction as it occurred. This does not include an AE that, if more severe, might have caused death
- The AE results in persistent or significant disability/incapacity. Disability means a substantial disruption of a person's ability to conduct normal life functions
- The AE requires or prolongs hospitalization Inpatient hospitalization is defined as any stay in the hospital of more than 24 hours, or any admission to a hospital ward or unit as an inpatient.
- The AE is an important medical event. Important medical events may meet serious criteria should the Investigator assess that they may significantly jeopardize the patient, represent a significant hazard, or require medical/surgical intervention.

As below, we will contact to the participants at 48-96 hours and 6-8 days after enrollment. At that time, we will collect below information.

Side effect(day2)

LOCAL

Erythema(y/n)

Induration(y/n)

Tenderness(y/n)

SYSTEMIC

Fever(defined as higher than and equal to 38.3 degrees Celsius)(y/n)

Gastrointestinal(diarrhea or nausea) (y/n)

IRB Study Number: 20210641
Version #4, Date: October 26, 2021

Arthralgia(y/n)
Fatigue(y/n)
Muscle ache(y/n)

Side effect(day7)
LOCAL
Erythema(y/n)
Induration(y/n)
Tenderness(y/n)

SYSTEMIC

Fever(defined as higher than and equal to 38.3 degrees Celsius)(y/n)
Gastrointestinal(diarrhea or nausea) (y/n)
Arthralgia(y/n)
Fatigue(y/n)
Muscle ache(y/n)

Within 6months post vaccination
Hospitalization(y/n, reason for admission)
COVID-19(y/n, if yes, date of diagnosis, symptom at the time of diagnosis)
Rejection(y/n)(if yes, type of rejection, date)
CMV infection(y/n)
BK infection(y/n)

27) Protocol Compliance

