The purpose of this study is to investigate the efficacy of the vaccines as a booster dose for COVID-19 in solid organ transplant recipients. The aims and objectives of this study is to check the immunogenicity after booster dosing of adenovirus vector vs. mRNA vaccine as a third dose. We are also going to investigate the safety of the third dosing after completion of two doses of mRNA vaccine.

Hypothesis of this study:

Booster dosing with mRNA vaccine should result in a higher rate of immunogenicity, defined as positive IgG, as compared to Adenovirus vector vaccine in solid organ transplant recipients who completed two doses of mRNA vaccine series.

2) **Background***

Severe acute respiratory syndrome coronavirus 2 (SARS-CoV-2), the etiology behind the coronavirus disease 2019 (COVID-19) worldwide pandemic, has resulted in significant mortality rates worldwide. Among immunocompromised hosts, such as solid organ transplant (SOT) recipients, several reports have indicated a significantly higher hospital admission rate and mortality^{1,2}; hence the need to provide robust protection in this vulnerable population.

IRB Study Number: 20210641
Version #4, Date: October 26, 2021

Since the beginning of the pandemic, several vaccines have been developed that have demonstrated a significant response in the general population in terms of immunogenicity and efficacy^{3,4}. This has been developed to hopefully revolutionize the fight against the COVID-19 pandemic^{5,6}.

It is well known from prior studies that vaccine immunogenicity in other viruses, such as influenza, is diminished in SOT recipients due to immunosuppressive medications⁷, as compared to general population. Thus, there have been several attempts to improve vaccine efficacy and/or immunogenicity in this special population, such as use of high dose vaccines⁸ and boosted doses⁹.

Even though a high efficacy of COVID-19 vaccines has been documented in the general population, there is some concern of low immunogenicity among SOT recipients of the SARS-CoV-2 vaccines¹⁰. At the same time, several reports have already documented breakthrough infection after vaccination in SOT recipients¹¹. Thus, we need to develop a better way to protect this vulnerable population with an efficient vaccine strategy.

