Already, there are several reports of increased immunogenicity with additional dosing of vaccination¹². Randomized controlled trial comparing placebo vs. other mRNA vaccine as a booster dose study showed some benefit¹³. However, as of now, there is no comparison study between mRNA and adenovirus vector vaccine. This time, we are conducting single center randomized controlled trial comparing mRNA vs. Adenovirus vector vaccine as a third dose after completion of two doses of mRNA vaccine in solid organ transplant recipients.

3) Inclusion and Exclusion Criteria*

Inclusion Criteria:

- *Patients 18 years of age and older*
- *Patients who had received a solid organ (kidney, liver, lung, heart, and pancreas) transplant patient from living or deceased donors.*
- *Patients with active graft with at least one immunosuppressive medication*
- *Completed two doses of BNT162b2 vaccination at least 28 days ago*

Exclusion Criteria:

- *Patient with non-active graft*
- *Any significant side effect with previous COVID-19 vaccination*
- *Within 28 days of BNT162b2 vaccine completion*
- *Already received more than and equal to three doses of COVID-19 vaccination*
- *Previously received COVID-19 vaccine other than BNT162b2 vaccine*
- *Previously received monoclonal Antibody treatment that are specifically directed against the spike protein for SARS-CoV-2 such as Mab, Bamlanivimab, etesevimab, Casirivimab, imdevimab, Sotrovimab and/or any combination.*

IRB Study Number: 20210641
 Version #4, Date: October 26, 2021

- *Thrombocytopenia (listed as a medical diagnosis or less than 50,000 per microliter 30 days prior vaccination)*
- *History of Capillary Leak Syndrome*
- *Adults unable to consent*
- *Individuals who are not yet adults (younger than 18 year old)*
- *Vulnerable patients (prisoners)*
- *Pregnant women*

4) Evaluation

Evaluation will be conducted as below schedule.

Procedures	Screening	Enrollment/Baseline Visit 1, Day 1	Phone Call Visit 2 48-96 hours	Phone Call Visit 3 6-8 days	Study Visit 4 Day 28 +/- 7 day	Study Visit 5 Month 6 (+/- 7 days)	Study Visit for Sub study only At Month 6 (+/- 30 days)
Informed consent	X	X					
Demographics	X	X					
Medical history	X	X					
Randomization	X	X					
Blood sample collection		X			X		X*
Vaccine Administration		X					
Symptom checker		X	X	X	X		
Phone call follow up			X	X	X	X	

* 50 optional participants only

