After obtaining consent, study team member, other than [name], will open the envelope to identify which vaccine to give. Each participant should be randomized and will receive one time dosing of either JNJ-78436735 or BNT162b2. After vaccination, those patients will need to stay Miami Transplant Institute outpatient clinic waiting area for 15minutes (+/- 2 minutes) to be monitored.

9) Discontinuation of patients:

- Patients may be discontinued under the following circumstances:
- A patient desire for discontinuation for any reason

IRB Study Number: 20210641
Version #4, Date: October 26, 2021

- Lost to follow up (every effort must be made to contact the patient)
- Death
- An Investigator's opinion that continuing the patient in the study is not appropriate

10) Study Timelines*

After consent is obtained, the blood draw for all patients will be done at the outpatient clinic phlebotomy room. After that, the participants will receive either vaccine. After vaccination, those patients will stay in the clinic for 15mins and if they have any symptoms, those patients will notify the research team. In the event of any severe reaction, the principal investigator will be notified immediately. Medical intervention will be address based on each case.

On visit 2, 48-96 hours after administration of the vaccine, the research team will call the patient to collect the side effect information. Again, visit 3, 6-8 days after enrollment, the research team will call the patient to collect side effect information. The participants will be back to the Miami Transplant Institute outpatient clinic in 28 (21-35) days from enrollment for follow-up blood collection. Upon follow up blood collection, the study team will ask the patient if they develop any symptoms after booster dosing.

We will also collect the blood test at 6 months (20-28 weeks) time period for those who are enrolled in the sub-study (50 patients will be enrolled)

11) Study Endpoints*

Primary endpoint is the anti-spike protein of SARS-CoV-2 virus IgG positive rate in one month after vaccination. Secondary endpoint includes the incidence rate of COVID-19 and the severity of COVID-19.

Safety endpoints includes side effect (i.e. pain at injection site, size of indwelling, fever, fatigue, and joint pain) at day 2 and 7 after vaccination. We also follow up to 6 months for any symptoms. This could also be gathered from the Jackson Health System medical record.

12) Procedures Involved*

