1.1.4 Time Period and Frequency for Event Assessment and Follow-Up

The occurrence of an adverse event (AE) or serious adverse event (SAE) may come to the attention of study personnel during study visits and interviews of a study participant presenting for medical care, or upon review by a study monitor.

All AEs will be captured on the appropriate case report form (CRF) as well as in the Adverse Event reporting section in Velos, a HIPAA AND 21 CFR part 11 compliant database and will be reported to the University of Miami’s IRB per institutional requirements.

Any medical condition that is present at the time that the participant is screened will be considered as baseline and not reported as an AE. However, if the study participant’s condition deteriorates at any time during the study, it will be recorded as an AE.

Changes in the severity of an AE will be documented to allow an assessment of the duration of the event at each level of severity to be performed. AEs characterized as intermittent require documentation of onset and duration of each episode.

Study personnel will record all reportable events with start dates occurring any time after informed consent is obtained until 7 (for non-serious AEs) or 30 days (for SAEs) after the last day of study participation. At each study visit, the investigator will inquire about the

IRB Study Number: 20210641
Version #4, Date: October 26, 2021

occurrence of AE/SAEs since the last visit. If the investigator should become aware of the development of cancer or a congenital anomaly in a subsequently conceived offspring of a female subject, including pregnancy occurring in the partner of a male study subject who participated in the study, this should be reported as an SAE adequately to Genentech drug Safety during follow up period. Events will be followed for outcome information until resolution or stabilization.

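### The day 2 and day 7 side-effect items do not separate new from standing symptoms, and the Day 1 symptom check that could do so has no stated timing or content

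*Combined protocol and SAP*

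**What the plan says.** The opening purpose statement gives a safety aim for the third dose itself: to "investigate the safety of the third dosing after completion of two doses of mRNA vaccine". Section 11 (Study Endpoints) turns this into an endpoint: "Safety endpoints includes side effect (i.e. pain at injection site, size of indwelling, fever, fatigue, and joint pain) at day 2 and 7 after vaccination".

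The data fields are listed in Section 26, under Serious Adverse Events, introduced by: "we will contact to the participants at 48-96 hours and 6-8 days after enrollment. At that time, we will collect below information". Each call has the same eight yes/no items: erythema, induration, tenderness, fever (38.3 °C or higher), gastrointestinal symptoms, arthralgia, fatigue and muscle ache. There is no field for onset, severity or change from the patient's usual state.

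Three other places bear on a baseline:

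- The schedule in Section 4 has a row "Symptom checker", marked at Visit 1 (Day 1), at both phone calls and at Day 28. Its content is not given, nor its position relative to the Day 1 injection.
- Section 10 (Study Timelines) describes one symptom step on Day 1: "After vaccination, those patients will stay in the clinic for 15mins and if they have any symptoms, those patients will notify the research team".
- Section 1.1.4 sets the adverse event rule: "Any medical condition that is present at the time that the participant is screened will be considered as baseline". Such a condition is not reported as an adverse event unless it deteriorates.

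The statistical text in Section 14 defines the safety population as everyone who received the study vaccine. It gives no rule for symptoms present before the dose and specifies no safety test.

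**The concern.** Participants are solid organ transplant recipients on at least one immunosuppressive drug. Some may already have fatigue, aches or diarrhoea when they enrol. If such a patient answers yes on day 2, the recorded data cannot show whether the symptom followed the vaccine.

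This matters because the stated aim concerns the safety of the third dose, and both arms receive a vaccine. Randomisation supports the comparison of one vaccine with the other, but it gives no reference for how much symptom burden either dose adds. The patient's own state before the injection is the natural reference, and the plan does not clearly secure it.

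Section 16 (Risks to Subjects) expects side effects to be low in this population because of immunosuppression. The lower the true induced rate, the larger the share of recorded yes answers that would be background.

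**Working it through.** **Can the baseline rule be applied to the checklist?** Applying Section 1.1.4 to an item needs two facts: whether the symptom was present before the dose, and whether it has since worsened.

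- Prior state: the only Day 1 symptom step in the text comes after the injection and depends on the patient volunteering a symptom. The Visit 1 mark in the schedule could be a pre-injection check or could be that same observation period. Medical history is taken at screening and baseline, but is not said to cover these eight items.
- Worsening: a yes/no item cannot show it, and neither can a pair of yes/no items. A patient with fatigue before and worse fatigue after answers yes both times.

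So the fields described do not supply what the rule needs, and no text links the rule to them.

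**Which items are exposed?** Fatigue, arthralgia, muscle ache and gastrointestinal symptoms can be standing complaints. Fever of 38.3 °C or higher and the three local signs are unlikely to be. Of the exposed items, fatigue and joint pain are named in the Section 11 endpoint.

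**Size.** The plan states no side-effect rates, so there is no figure to reproduce. All values of b and r below are assumptions.

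Let b be the background prevalence, equal in both arms on average through 1:1 randomisation. Let r be the vaccine-induced rate, independent of b. If every standing symptom is recorded as yes:

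- Recorded rate = 1 - (1-b)(1-r) = b + (1-b)r
- Inflation = b + (1-b)r - r = b(1-r)
- Recorded difference = (1-b)(r2 - r1)

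With r1 = 20% and r2 = 30%, a true difference of 10 points:

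| b | Recorded, r1 | Recorded, r2 | Difference |
|---|---|---|---|
| 5% | 0.05 + 0.95 × 0.20 = 24% | 0.05 + 0.95 × 0.30 = 33.5% | 9.5 points |
| 10% | 0.10 + 0.90 × 0.20 = 28% | 0.10 + 0.90 × 0.30 = 37% | 9 points |
| 20% | 0.20 + 0.80 × 0.20 = 36% | 0.20 + 0.80 × 0.30 = 44% | 8 points |

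The inflation is less than b itself. At b = 20% it is 0.20 × 0.80 = 16 points in one arm and 0.20 × 0.70 = 14 points in the other.

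If induced rates are low, as Section 16 expects, background dominates. With r = 5% and b = 10%, the recorded rate is 0.10 + 0.90 × 0.05 = 14.5%, and 10 of those 14.5 points are patients who already had the symptom.

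**Effect on a comparison.** The plan specifies no safety test, so this is illustration only. Take 100 per arm (200 enrolled, 1:1), two-sided 5% level, and true induced rates of 40% and 20%.

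- No background: 40% vs 20%, power 0.88.
- b = 20%, raw yes/no: 52% vs 36%, difference 16 points, power 0.63.
- b = 20%, only new symptoms counted among the 80 per arm who were symptom-free: 40% vs 20%, power 0.79.

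If the two induced rates are equal, the recorded difference is (1-b) × 0 = 0 at every b. Background creates no false difference.

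**The case against.** The strongest reply is that the baseline is already provided for. The schedule marks the symptom check at a visit labelled baseline, in the same row as the two calls, so one instrument used at every marked visit is a plausible reading. Section 1.1.4 limits recording to events starting after consent and has the investigator ask at each study visit about events since the last one. Section 1.1.2 requires start and end dates and a causality judgement for each adverse event. The checklist is headed as side effects and is a list of fields, not a call script, so a caller may well ask only about new symptoms.

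Part of this stands. A reader might infer that there is no pre-injection assessment at all, or that chronic symptoms will certainly be scored as side effects. The documents support neither. The Visit 1 mark makes the baseline ambiguous rather than absent, and nothing instructs staff to record a standing symptom as yes. But nothing prevents it either, and the adverse event rules are not tied to the checklist answers that form the endpoint.

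It is also true that the effect on the between-arm comparison is modest in the first illustration (0.5 to 2 points out of 10), and that three local items and fever are barely touched.

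**Conclusion.** The point holds as an avoidable ambiguity in how the safety endpoint is measured. Per-arm rates for fatigue, joint pain, muscle ache and gastrointestinal symptoms can be inflated by up to b(1-r), and a true between-arm difference can be diluted by the factor (1-b). This rests on equal background in the arms, independence of background and induced symptoms, and standing symptoms being recorded as yes. The documents give no background prevalence, so the size in this trial cannot be stated.

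Three further inferences are not supported:

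- A reader might conclude that the safety comparison is biased toward one vaccine. With randomised arms it is diluted, not tilted, and the primary IgG endpoint is untouched.
- A reader might combine the systemic items into a large any-symptom background rate. The plan defines no such composite, fever should not be in it, and independence of fatigue, joint pain and muscle ache is doubtful.
- A reader might say that the undated CMV and BK fields in the six-month list have the same fault. They sit under a post-vaccination heading, are not named as safety endpoints in Section 11, and onset may be recoverable from the medical record.

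The change is still worth making, because answers about the state before the dose cannot be reliably recovered once the patient has been vaccinated.

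**What to change.** 1. In Sections 4 and 10, state that the Visit 1 symptom check is completed before the injection and uses the same eight items as the calls.
2. Add to each item at the day 2 and day 7 calls a yes/no question on whether it is new or worse since vaccination. This is needed because worsening cannot be derived from two presence answers.
3. In Section 11, define the safety endpoint for each item as absent before the injection and present afterwards, or reported as worse. Report the raw yes rate alongside.
4. In the statistical text of Section 14, state that baseline-positive answers are handled by that definition.

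The cost is a few extra minutes at a visit already marked for the symptom check, one added question per item at the calls, and slightly lower headline side-effect rates. Adding onset dates to the CMV and BK fields, as COVID-19 and rejection already have, is optional tidying.

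### Fever is defined by a reading of at least 38.3 C but collected by phone as yes or no, with no recorded value and no way to mark a temperature as not measured

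*Combined protocol and SAP*

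**What the plan says.** Section 11 (Study Endpoints) lists fever among the safety endpoints: "fever, fatigue, and joint pain) at day 2 and 7 after vaccination". Section 10 (Study Timelines) makes the first contact a phone call, "On visit 2, 48-96 hours after administration of the vaccine, the research team will call the patient to collect the side effect information", and the second likewise, "Again, visit 3, 6-8 days after enrollment, the research team will call the patient to collect side effect information". The checklists themselves follow the Serious Adverse Events definitions and are introduced with "As below, we will contact to the participants at 48-96 hours and 6-8 days after enrollment". On both the day 2 and the day 7 list the item reads "Fever(defined as higher than and equal to 38.3 degrees Celsius)(y/n". It is the only item on either list that is defined by an instrument reading.

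The visit schedule in section 4 (Evaluation) has rows for a symptom checker and for phone follow-up, but none for a diary or a temperature. Section 7 (Description of the study) blinds the patient and the laboratory but not the study team. The statistical text at the end of section 14 (Data Management) defines the safety population as everyone vaccinated. It gives no rule for a symptom whose status is unknown.

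**The concern.** A yes/no answer to a threshold question is only as good as the reading behind it. Nothing in the plan asks patients to take their temperature, and nothing records whether they did. A caller who speaks to a patient who felt hot but took no reading has three choices: enter no because the threshold was not shown, enter yes on the patient's impression, or leave the field blank. The plan does not choose among them. With no value kept, the data cannot later show which choice was made.

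What is at stake is the fever rate in each arm and the comparison of tolerability between the two vaccines. The plan allows callers to know the allocation, so unmeasured cases could be resolved differently in the two arms. A reading that was never taken or written down cannot be reliably recovered afterwards.

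**Working it through.** **Inputs from the documents.** The threshold and yes/no field (checklists under Serious Adverse Events), the phone mode (section 10), the endpoint status (section 11) and the unblinded study team (section 7). The plan states no fever rate, no share of patients without a reading and no coding rule, so there is no figure of its own to reproduce. Every rate below is an assumption, used only to see which way the error could run.

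**Step 1: three ways to enter an unmeasured patient.** Let *t* be the true fever rate and *u* the share unmeasured, with measuring unrelated to fever.

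- (a) Entered as no: recorded rate = t(1 − u).
- (b) Left blank and excluded: recorded rate = t.
- (c) Answered by feel, with assumed sensitivity 0.8 and false-positive rate 0.1: recorded rate = t(1 − u) + u[0.8t + 0.1(1 − t)].

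With t = 10% and u = 30%:

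- (a) 0.10 × 0.70 = 7.0%.
- (b) 10.0%.
- (c) 0.07 + 0.30 × (0.08 + 0.09) = 0.07 + 0.051 = 12.1%.

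For t from 5% to 20% and u from 10% to 50%, (a) gives 2.5% to 18%, always below the truth. Rule (c) gives 5.9% to 22%, above the truth in every case tried. Under (c) the rate is overstated whenever 0.8t + 0.1(1 − t) > t, that is, whenever t is below 0.1/0.3, or about 33%. The direction of error thus depends on a rule that the plan does not give.

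**Step 2: different handling by arm.** Take t = 10% and u = 30% in both arms. If rule (a) were used throughout one arm and rule (c) throughout the other, the recorded rates would be 7.0% and 12.1%. That is a difference of 5.1 points where none exists. This is an extreme case, meant to show the mechanism.

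**Step 3: measuring that depends on fever.** People who feel hot are plausibly more likely to measure. Suppose 90% of febrile and 40% of afebrile patients take a reading, and true fever is 20% in one arm and 8% in the other.

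- Confirmed fever among everyone contacted: 0.20 × 0.90 = 18.0%, and 0.08 × 0.90 = 7.2%.
- Fever among measured patients only: 0.18 / (0.18 + 0.80 × 0.40) = 0.18 / 0.50 = 36%, and 0.072 / (0.072 + 0.92 × 0.40) = 0.072 / 0.44 = about 16%.

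Under these assumptions the rate restricted to measured patients is much further from the truth than the rate among all contacted. This bears on how the improved item should be reported.

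**The case against.** A reader might infer that an unmeasured patient can only be entered as no, so that fever is necessarily understated. The documents do not support that. They contain no such coding rule, and a yes given on feeling is possible. So is a blank: section 1.1.1 describes system checks for incomplete data.

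A reader might also infer a loss of power for comparing fever between the arms. The statistical text assigns the χ² test to vaccine response and to factors affecting seroconversion. For safety it states only the population. There is no planned fever test and no fever power target to erode.

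It can fairly be said that the checklist in the protocol is not the case report form itself, which is not available here, and that symptoms are sought elsewhere. The symptom checker runs at four contacts, symptoms are asked about again at the day 28 visit, and sections 1.1.4 and 1.2 call for adverse-event inquiry at each visit and open questioning. Section 11 adds, after the six-month symptom follow-up, "This could also be gathered from the Jackson Health System medical record". These routes mean that a patient who felt feverish is not necessarily lost. None of them secures a home temperature or shows that none was taken, so the gap in the defined endpoint remains.

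Finally, no passage indicates that callers do treat the arms differently. That stands: differential handling is a possibility left open by the design, not a demonstrated bias.

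**Conclusion.** The point holds as a gap in data collection. The plan defines fever by a reading and then collects it in a form that cannot separate patients without fever from patients without a reading. Staff who are not blinded are left to settle those cases. Misclassification may run in either direction and may differ between the arms.

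Its size is unknown. The illustrative figures rest wholly on assumed fever rates, measuring shares and accuracy of feel, and they establish only that the direction depends on an unstated rule. The point touches one safety endpoint among several and has no bearing on the primary IgG comparison or the sample size. It is a low-priority improvement, worth making because it costs almost nothing and cannot be made retrospectively.

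**What to change.** On both the day 2 and the day 7 checklist, replace the yes/no item with: *Highest temperature measured since vaccination / since last call: ____ C, or not measured.* Keep the planned 38.3 C definition and apply it to the recorded value at analysis, so that the caller no longer makes the classification.

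In the safety table:

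- Main row: confirmed fever (a recorded reading of at least 38.3 C) among all vaccinated patients contacted at that call, described as confirmed fever because unmeasured cases are not counted.
- Number not measured, by arm.
- Sensitivity row: the rate among patients with a reading, with a note that selective measuring may inflate it, as the third step of the working shows.

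The cost is one form field on two checklists and one extra table row. No visit, procedure or clinical rule changes.
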